5.2.1 Explanation for choice of comparators

If this study demonstrates CASP to be a better predictor of left ventricular mass and therefore cardiovascular risk in young people than simple classification as stage 1 hypertension according to brachial BP, it follows that reducing CASP should regress left ventricular mass commensurate with a reduction in brachial BP. To investigate this, a randomised clinical trial will be undertaken in those identified to be in the highest quartile of CASP values from a cohort of people diagnosed with stage 1 hypertension. The active intervention will be BP lowering treatment, using anti-hypertensive treatments recommended by NICE guidance ⁽⁴⁾ and licensed for use in this age group – see section 6.4. The comparator is no treatment, which represents recommended usual care for patients with stage 1 hypertension and no other concurrent cardiovascular disease or overt target organ damage. These treatment regimens represent national guideline recommended approaches for the treatment of stage 1 hypertension in young people and are appropriate for use in this study. The use of no treatment as a comparator represents 'usual care' and avoids the unnecessary administration of placebo.

5.2.2 Study Hypotheses and Outcomes:

 We hypothesise that the non-invasive measurement of CASP will better define and stratify which younger people (18-54yrs) with stage 1 hypertension, according to their brachial BP, will have evidence of target organ damage as detected by MRI. We propose that those with the highest CASP values will have evidence of damage and are truly hypertensive, whereas those with the lowest CASP values will have no damage, are truly normotensive and are misclassified as hypertensive according to their brachial BP values.

- We hypothesise that the non-invasive measurement of CASP in younger people with stage 1 hypertension will better define who requires treatment. We propose that only those with high CASP values will have evidence of early cardiovascular structural damage and thus require treatment and that there will be no development of target organ damage in those with low CASP values if left untreated for 1 year.
- We hypothesise that those with high CASP values will exhibit evidence of pressure-mediated cardiovascular structural damage, and that this damage will regress with treatment targeted at reducing CASP for one year, confirming the benefits of treatment in those with high CASP values.

5.2.3 Key Research Questions:

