5.3 Trial Design

This study is a single centre study in two stages with a STOP/GO checkpoint between stages. The first stage (STAGE 1) of the study will comprise a screening study for 18 months, in which 500 young men with stage 1 hypertension and no other evidence of cardiovascular disease will be stratified into two groups according to non-invasive measurement of their central aortic blood pressure (the LOW and HIGH CASP groups). The second stage of the study (STAGE 2) will comprise a 12 month RCT in the HIGH CASP cohort (treatment versus no treatment) utilising a Prospective Randomised Open Blinded Endpoint (PROBE) design ⁽⁵⁰⁾. The second stage of the study will also comprise a 12 month observational follow-up study of the LOW CASP cohort which will run in parallel with the RCT. The decision to proceed to STAGE 2 (STOP/GO checkpoint) will depend on whether the first part of our hypothesis is proven, i.e. that CASP will differentiate between those with and without cardiovascular structural damage (i.e. increased left ventricular mass index), measured using cMRI.

6. Methods

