A STOP/GO checkpoint has been incorporated into the study design which will be evaluated before the study proceeds to the second stage. The STOP/GO checkpoint will be implemented to avoid futility in implementing the second part of the study i.e. if there is no difference in cardiac structure between the HIGH and LOW CASP cohorts there would be little likely benefit in stratifying participants by their central BP for subsequent treatment for blood pressure lowering.

Cardiac MRI (cMRI) will be used to measure left ventricular mass index in participants from the HIGH and LOW CASP groups participating in the stage 1 screening study. This data will be used to evaluate

the STOP/GO checkpoint. If a difference in LVMI is observed between participants from the HIGH and LOW CASP groups, the null hypothesis that there is no difference in LVMI between groups will be rejected and the study can proceed to the second stage. If the null hypothesis is not rejected i.e. if there is no difference in LVMI between people from the HIGH and LOW CASP groups, the TREAT CASP study will be terminated at this point. This evaluation will be used to confirm or refute the first key element of our hypothesis, i.e. whether CASP has been effective at identifying patients with and without pressure-related target organ damage, irrespective of their brachial blood pressure values.

The decision to proceed to the second stage of the study will be taken by the Trial Steering Committee. The data upon which the STOP/GO decision is made will be reviewed by an independent statistician who will provide recommendations to the Trial Steering Committee.

6.3.1.10 STAGE 2 Randomised Clinical Trial and Observational Follow-up Study:

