If the conditions of the STOP/GO checkpoint are met i.e. if stratification by CASP value identifies groups with differing pressure related cardiac damage (LVMI), the study will proceed to the second stage. The second stage of the TREAT CASP study incorporates a 12 month randomised controlled trial in the HIGH CASP group using a prospective, randomised, open label, blinded end-point (PROBE) design ⁽⁵⁰⁾. The RCT is designed to evaluate whether people from the HIGH CASP group benefit from BP lowering drugs compared to no treatment (usual care) with regard to regression of their baseline cardiovascular structural damage (elevated LVMI relative to the LOW CASP group). The degree of regression of cardiovascular structural damage (LVMI) between the intervention and the usual care groups constitutes the primary outcome for the TREAT CASP study and will be evaluated following completion of the RCT (after 12 months treatment) following a repeated cMRI evaluation.

The second stage of this study also incorporates an observational follow-up of the LOW CASP group (n=65) with repeat cMRI after 12 months. This is designed to evaluate whether there is any development or progression of cardiovascular structural changes if people with LOW CASP are left untreated for 12 months.

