The inbuilt STOP/GO checkpoint to allow the study to proceed to the RCT (stage 2) is based on achieving a significant difference in LVMI as measured by MRI between people in the HIGH CASP and LOW CASP groups at the end of the screening phase (stage 1 see section 6.3.1.7).

Previously published studies indicate that LVMI is directly related to blood pressure and that the relationship between the change in systolic blood pressure and the change in LVMI approximates to the order of $1g/m^2$ LVMI per mmHg SBP ^(57,58). This order of magnitude of change is similar to that seen for the regression in LVMI with BP-lowering treatment in the analysis of published studies for the RCT power calculation (average reduction in SBP -8 mmHg, average reduction in LVMI with treatment -6.6 g/ m^2). Preliminary data from our clinical laboratory in men with stage 1 hypertension stratified by their CASP values indicates that groups incorporating the highest and lowest 25% of the population with regard to their CASP values are separated by brachial systolic blood pressures of at least 10mmHg [Appendix, figure 7]. Based on the relationship between LVMI and BP as outlined above, this indicates a likely separation between groups in LVMI of approximately $10g/m^2$. With regard to a starting value, systematic review of LVMI values by MRI in 1,032 young men from 11 published studies indicates a mean value of 78.5 g/m², SD 11.8g/m² ($^{59-67}$). Combining an estimated 10g/m² difference between the HIGH and LOW CASP groups with the SD for LVMI in young men, indicates a sample size of 31 per group would be required to demonstrate a difference in LVMI with 90% power at p=0.05. This indicates that a sample size of 65 individuals in the LOW CASP and 130 individuals for the HIGH CASP group should have abundant power to demonstrate a difference in LVMI at the study STOP/GO checkpoint. This will provide a robust basis to confirm or refute our hypothesis that CASP provides an effective mechanism for identifying patients with and without pressure-related target organ damage, in people with a diagnosis of stage 1 hypertension.

6.7.2.1 Consideration of variability in LVMI:

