of the models. Thus, only coefficients that significantly improve the fit of the models or where a strong case for their known biological importance can be made will be included. Results will be presented in a multi-stage format so that readers can assess the unadjusted and adjusted models separately. Where predictor variables are suspected to have a non-linear influence on outcome (e.g. on LV mass index), further polynomial terms may be added (e.g. quadratic and cubic) but careful examination of model fits to raw data will be made to prevent such models from over-fitting the data in a spurious sense. Where interactions between predictor variables are suspected on the basis of biological plausibility e.g. varying influence of adiposity on LV mass index with age, the appropriate interaction terms will be added to the models to assess this. Outliers will be dealt with on a case-by-case basis and excluded if values are biologically implausible or can be found to be erroneous after reference to the raw data.

No interim analyses will be performed in accordance with the blinded nature of the study. Results will be reported as per CONSORT guidelines ⁽⁸⁷⁾.

6.10.4.2.1 Data Manipulation:

In all cases, parametric analyses will be preferred and applied to data with normal distributions or after appropriate transformation to normality e.g. Log transformation for right-skewed data.

6.10.4.2.2 Missing Data:

For missing data appropriate procedures will be used such as multiple imputation procedures or (where y-values are (MAR) missing at random), the bootstrap approach as suggested by Efron ⁽⁸⁶⁾.

6.10.4.2.3 Analysis of the STOP/GO Checkpoint:

It is a STOP/GO condition of the study prior to stage 2 that the high and low CASP groups must have a significant (P<0.05) difference in LV mass index. Student t-test comparison of the groups will be used to assess this.

6.10.4.2.4 Economic evaluations:

No economic evaluations are planned. Evaluation of cost effectiveness of the study medications in terms of quality adjusted life years (QALYs) is well established ⁽⁴⁾.

6.10.4.2.5 Additional Analyses – Subgroup:

No additional analysis in sub-groups is planned.

6.10.4.2.6 Additional Analyses - Adjusted:

No additional analysis in sub-groups is planned.

6.10.4.2.7 Analysis Population and Missing Data:

The analysis population and strategies for dealing with missing data are outlined in section 6.10.4.2 – statistical methods.

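### The STOP/GO t-test can show that mean LVMI differs between HIGH and LOW CASP men, but not, as the protocol says, that CASP separates men with damage from men without it

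*Protocol*

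**What the plan says.** **The hypothesis (section 5.2.2)** is stated for each group in absolute terms. For HIGH CASP: "those with the highest CASP values will have evidence of damage and are truly hypertensive". For LOW CASP: "whereas those with the lowest CASP values will have no damage, are truly normotensive and are misclassified as hypertensive".

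**The design (section 5.3)** makes progress to stage 2 depend on whether "CASP will differentiate between those with and without cardiovascular structural damage (i.e. increased left ventricular mass index" is shown by cardiac MRI. It does not say what the increase is measured against.

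**The rule (section 6.10.4.2.3)** is that "the high and low CASP groups must have a significant (P<0.05) difference in LV mass index", assessed by Student's t-test. No direction or size is given.

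**The conclusion attached to the rule.** Section 6.3.1.9 says the evaluation will decide "whether CASP has been effective at identifying patients with and without pressure-related target organ damage". Section 6.7.2 says much the same, and calls the comparison a robust basis for accepting or rejecting that hypothesis.

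**The description of what is to be regressed (section 6.3.1.10)** is "baseline cardiovascular structural damage (elevated LVMI relative to the LOW CASP group". Section 6.4.8 then takes the LOW CASP level as the yardstick for regression in the treated arm.

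**The only outside LVMI figure** is in section 6.7.2: "systematic review of LVMI values by MRI in 1,032 young men from 11 published studies indicates a mean value of 78.5" g/m², SD 11.8 g/m². It is a starting value for the sample size and is not used as a comparator.

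**The concern.** The hypothesis says where each group stands: one damaged, one not. The test says only how far apart the groups are. The same pass would arise if both groups were above normal, with HIGH further above, or if HIGH were at the normal mean and LOW below it.

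The protocol's planning model makes this a practical matter. Section 6.7.2 takes LVMI to rise by about 1 g/m² per mmHg of systolic pressure, and derives the expected 10 g/m² from a brachial systolic separation of at least 10 mmHg. A steady gradient of that kind produces a difference between the two ends of any blood pressure distribution, with no threshold below which the heart is normal. All the men scanned have stage 1 hypertension, so no scanned group fixes the normal level.

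At stake is the interpretation of a pass. Taken as sections 6.3.1.9 and 6.7.2 word it, a pass would be reported as evidence that LOW CASP men are free of structural damage and wrongly labelled hypertensive. Section 5.1.8.1 lists that as a benefit of using CASP.

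**Working it through.** **Inputs.** Difference 10 g/m², SD 11.8 g/m², 90% power, P=0.05, 31 per group, actual groups of 65 LOW and 130 HIGH (all section 6.7.2). Test: two-sample t-test, taken as two-sided (section 6.10.4.2.3).

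**Step 1: reproduce the plan's figure.** n per group = 2 × (1.960 + 1.282)² × (11.8/10)² = 29.3, so 30 by the normal approximation. The noncentral t calculation gives 30.25, rounded up to 31. The stated 31 is correct.

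**Step 2: standard error at the actual sizes.** SE = 11.8 × √(1/65 + 1/130) = 1.79 g/m².

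**Step 3: smallest observed difference that passes.** t(193) × SE = 1.972 × 1.79 = 3.5 g/m². With the 50% larger SD that section 6.7.2.1 allows for (17.7), it is 5.3 g/m².

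**Step 4: chance of a pass for a true 10 g/m².** 10/1.79 = 5.58, and Φ(5.58 − 1.96) = 0.9998. The group means do not enter the formula; only their difference does. Simulation (20,000 trials per setting) agrees. For LOW means of 58.5, 68.5, 78.5, 88.5, 98.5 and 108.5 the pass rate was above 99.9% each time. For a 6 g/m² difference it was 91.1% to 91.5% at every location.

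**Step 5: what the same pass can mean.** The protocol gives no upper limit of normal. For illustration only, assume 78.5 + 1.96 × 11.8 = 101.6 g/m².

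| LOW mean | HIGH mean | Pass rate | LOW above 101.6 | HIGH above 101.6 |
|---|---|---|---|---|
| 68.5 | 78.5 | >99.9% | 0.2% | 2.5% |
| 78.5 | 88.5 | >99.9% | 2.5% | 13.3% |
| 88.5 | 98.5 | >99.9% | 13.3% | 39.5% |

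The percentages depend on the assumed limit. With HIGH at 78.5, the share above it runs from 15.9% (limit at mean + 1 SD, 90.3) to 2.3% (mean + 2 SD, 102.1). The pass rate does not depend on it. The table shows what the test cannot distinguish; it does not say which row is likely.

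**Step 6: direction.** As worded, the rule names no sign. A true difference of 10 g/m² the other way also gives P<0.05 in at least 99.98% of simulated trials.

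**Step 7: does anything else fix the baseline state?**
- ECG hypertrophy and other overt damage on routine testing are excluded in both groups (sections 6.3.1.3 and 6.7.2.1).
- The secondary markers in section 6.5.2 carry no limits for damage.
- The 12-month LOW CASP follow-up (section 6.3.1.10) looks for development or progression. A raised but stable LVMI would show no progression.

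**The case against.** **The gate does its operational job.** Section 6.3.1.9 gives its purpose as avoiding a futile second stage: if LVMI does not differ, stratifying by CASP has little to offer. A relative test suits that purpose. This stands. So does the point that the primary outcome (section 6.5.1) is a randomised comparison of LVMI change and needs no definition of damage.

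**The wording in section 6.3.1.10 is not a formal definition.** A reader might infer that the protocol defines damage as LVMI above the LOW group, which would make LOW men undamaged by construction. The text does not go that far. The parenthesis describes what the trial hopes to regress in HIGH CASP men; section 5.3 speaks only of increased LVMI, and section 6.5.2 lists other markers of damage. The phrase is still misleading and should go.

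**The LOW CASP claim does not rest on the t-test alone.** Section 5.1.8.2 accepts that LOW CASP men may prove not to be truly normotensive, and the repeat scan examines this. No treatment is already described as usual care for all these men, so the test does not alter the management of LOW men within the trial. Both points reduce the consequence. Neither supplies evidence on baseline damage.

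**A formal second hurdle is tempting, but the documents do not support one.** One could require the upper 95% limit of the LOW mean to lie within, say, 5 g/m² of 78.5. That margin has no source in the protocol. The cited reference series include athletes and hypertensive patients, and study-level values are not shown. The rule is also fragile: both conditions would be met in about 92% of trials if LOW equals 78.5, but in about 52% if LOW is 2 g/m² higher, a shift that a scanner difference might produce.

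**Reference ranges may be left to the SAP.** That is fair for reporting. The inference from the test, however, is stated in the protocol, and that statement is what needs correcting.

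**Conclusion.** The point holds as a wrong inference written into the plan; the sample-size arithmetic is sound. A pass shows that mean LVMI differs between HIGH and LOW CASP men. It does not show that LOW men have no damage or that HIGH men have any. With 130 v 65 men, SD 11.8 g/m² and approximately normal data, a 10 g/m² difference passes in more than 99.9% of trials at any location on the LVMI scale, and an observed 3.5 g/m² suffices.

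Two stronger readings go too far. A reader might infer that the STOP/GO design or the randomised trial is invalid; neither is. A reader might also convert the pass rates into a rate of false conclusions about LOW men. The documents do not support that, because it would depend on where the LOW mean truly lies, which they do not tell us. LOW men may well be normal; this test cannot say.

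**What to change.** 1. Keep the t-test in section 6.10.4.2.3 as the GO rule.
2. In sections 6.3.1.9 and 6.7.2, limit its conclusion to: *mean LVMI is higher in HIGH than in LOW CASP*. Draw it only when the difference has that sign.
3. In section 6.3.1.10, replace the phrase about damage and its parenthesis with *LVMI*, so that the trial is described as assessing regression of baseline LVMI.
4. State that absence of damage, or true normotension, in LOW CASP men will not be concluded from this test.
5. Report the LOW and HIGH means with 95% CIs, descriptively and without a pass/fail margin, beside a suitable published normotensive male cardiac MRI reference, noting differences in scanner and sequence. At SD 11.8 the half-widths are about 2.9 g/m² for LOW (1.998 × 11.8/√65) and about 2.0 g/m² for HIGH (1.979 × 11.8/√130).

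The cost is a wording change and one extra summary from scans already planned, with no added participants or visits. The downside is a more cautious claim about LOW CASP men, and the comparison with published values will carry uncertainty from differences in method.

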6.4 Interventions

The active intervention for the stage 2 RCT is BP lowering using treatments recommended by NICE guidance ⁽⁴⁾ and licensed for use in this age group. The comparator is no treatment, which represents recommended usual care for these patients.

Active treatment will be titrated (dose/regimen adjusted) according to participants' CASP value rather than to the brachial BP value. Active treatment will be up-titrated to achieve a CASP value of <120mmHg and/or at least a 5mmHg reduction in CASP from baseline. For patients unable to tolerate higher dose medication, the treatment may be back-titrated to achieve the best CASP value tolerated.

6.4.1 Arm A

6.4.1.1 Products

BP lowering therapy for the intervention group in the stage 2 randomised clinical trial will be prescribed according to current NICE guidance for people aged <55years. Treatment constitutes an angiotensin receptor blocker (losartan 50mg once daily) for all ethnic groups other than for younger black men of African or Caribbean descent for whom a calcium antagonist (amlodipine 5mg once

daily) is the recommended initial treatment. Both of these treatments are well tolerated, generic and established medications, widely used in routine clinical practice.

Treatment will be titrated according to the CASP value rather than brachial BP values and up-titrated to achieve a CASP value of <120mmHg and/or at least a 5mmHg reduction in CASP from baseline. Combination therapy (i.e. angiotensin receptor blocker plus calcium antagonist) is also permitted if required in order to achieve blood pressure target.

6.4.1.2 Treatment Schedule

Participants in the stage 2 RCT randomised to active treatment will receive losartan 50 mg tablets once daily for 12 months. For participants of African or Caribbean descent treatment, participants will receive amlodipine 5 mg tablets once daily for 12 months.

6.4.1.3 Dispensing

All treatments will be prescribed via NHS standard prescriptions and will be sourced, stored and dispensed by the participant's local pharmacy. Payments will be made by NHS prepayment card which will be supplied to participants.

6.4.1.4 Dose Modifications, Interruptions and Discontinuations

Treatment may be up-titrated to Losartan 100mg tablets once daily and/or amlodipine 5mg tablets once daily may be added at the discretion of the study physician depending upon blood pressure achieved at follow-up visits during the 12 month treatment period. The study nurse will be permitted to prescribe the drugs. For patients unable to tolerate higher-dose medication, the treatment may be back-titrated to achieve the best CASP value tolerated. For participants of African or Caribbean descent treatment may be up-titrated to amlodipine 10mg tablets once daily and/or losartan 50mg tablets once daily may be added at the discretion of the study physician as above, but the study nurse will also be permitted to prescribe.

6.4.2 Arm B

6.4.2.1 Products

The comparator is no treatment, which represents recommended usual care for these patients.

6.4.2.2 Treatment Schedule

Not applicable, no trial-specific medicinal products will be taken on arm B.

6.4.2.3 Dispensing

Not applicable, no trial-specific medicinal products will be taken on arm B.

6.4.2.4 Dose Modifications, Interruptions and Discontinuations

Not applicable, no trial-specific medicinal products will be taken on arm B.

6.4.3 Accountability

Drug accountability will be by tablet count at patient visits. The study authors acknowledge the limitations in monitoring accountability by simple tablet count, but this represents the only practical way to estimate compliance in a community-based study with community pharmacy-based medication dispensing. Study medication is given within license and according to national guidelines – there are no anticipated medication safety issues. Given that participants are blood pressure

lowering-treatment naïve, the degree of separation in blood pressure between treatment arms will also give an indication of medication compliance.

